### 8. EFFICACY ANALYSES

### 8.1. Primary Efficacy Analyses

### 8.1.1. Endpoint / Variables

The primary efficacy analyses endpoint is the annualized rate of exacerbations.

### 8.1.2. Summary Measure

The frequency of exacerbations of asthma collected during the on-treatment phase (Appendix 3: Treatment Phases) will be summarised.

### 8.1.3. Population of Interest

The primary efficacy analyses will be based on the AT population, unless otherwise specified.

### 8.1.4. Strategy for Intercurrent Events

For the primary analyses, only on-treatment exacerbations will be summarised. More details about phases can be found in Appendix 3: Treatment Phases.

### 8.1.5. Statistical Analyses / Methods

Details of the planned displays are provided in Appendix 10: List of Data Displays and will be based on GSK data standards and statistical principles.

Unless otherwise specified, endpoints / variables defined in Section 8.1 will be summarised using descriptive statistics.

### 8.1.5.1. Statistical Methodology Specification

En	dpoint / Variables
•	Annualized rate of on-treatment exacerbations
Мо	del Specification
•	The frequency of exacerbations will be analysed using Negative Binomial generalised linear model.
•	Exacerbations separated by less than 7 days will be treated as a continuation of the same exacerbation.
•	The logarithm of time on treatment will be used as an offset variable.
Мо	del Checking & Diagnostics
•	Refer Appendix 8: Model Checking and Diagnostics for Statistical Analyses.
Мо	del Results Presentation
•	The estimated mean rate per year and corresponding 95% confidence interval will be presented

#### Sensitivity and Supportive Analyses

• An additional analysis will be performed only for the subjects enrolled into study 201312 from previous exacerbation study MEA115588. This analysis will present the exacerbation rate during the current and preceding study periods (from studies MEA115588 and MEA115661) to assess if the exacerbation rate reduction has been maintained.

### 8.2. Secondary Efficacy Analyses

### 8.2.1. Endpoint / Variables

The secondary efficacy analysis consists of:

- Time to First Exacerbation
- Annualized rate of Exacerbations Requiring Hospitalisation or Emergency Department (ED) visit
- Annualized rate of Exacerbations Requiring Hospitalisation
- Asthma Control Questionnaire-5 Score
- Forced expiratory volume in 1 second (FEV1)
- Oral Corticosteroid Dose (mg/day)

### 8.2.2. Summary Measure

The frequency of exacerbations requiring hospitalisation/hospitalisation or ED visit collected during the on-treatment phase (Appendix 3: Treatment Phases) will be summarised.

Asthma Control Questionnaire (ACQ-5) score (absolute value and change from baseline) and Pre-bronchodilator  $FEV_1$  (absolute value and change from baseline (mL)) will be summarised by visit.

Additionally, OCS use will be summarised only for the subjects enrolled into study 201312 from previous OCS reduction study MEA115575. This analysis will present the median OCS Dose (mg/day) during the current and preceding study periods (from studies MEA115575 and MEA115661) to assess if the reduction in OCS use has been maintained.

### 8.2.3. Population of Interest

The secondary efficacy analyses will be based on the AT population, unless otherwise specified.

### 8.2.4. Strategy for Intercurrent Events

Only subjects who have on-treatment data will be included.

### 8.2.5. Statistical Analyses / Methods

Details of the planned displays are provided in Appendix 10: List of Data Displays and will be based on GSK data standards and statistical principles.

Unless otherwise specified, endpoints / variables defined in Section 8.2.1 will be summarised using descriptive statistics and graphically presented (where appropriate).

### 8.2.5.1. Statistical Methodology Specification

### Endpoint / Variables

• Time to First Exacerbation

### **Results Presentation**

• Kaplan-Meier estimates will be summarised by study visit and presented graphically.

### Endpoint / Variables

- Annualized rate of Exacerbations Requiring Hospitalisation or Emergency Department visits
- Annualized rate of Exacerbations Requiring Hospitalisation

### **Results Presentation**

• See Section 8.1.5.1 for details of the analysis model.

### **Endpoint / Variables**

• Asthma Control Questionnaire-5 (ACQ-5) score

### **Results Presentation**

• ACQ-5 score (absolute value and change from baseline) will be summarised by visit.

### Endpoint / Variables

• Forced expiratory volume in 1 second (FEV1)

### **Results Presentation**

 Pre-bronchodilator FEV1 (absolute value and changes from baseline (mL)) will be summarised by visit.

### Endpoint / Variables

• Oral Corticosteroid Dose (mg/day)

### **Results Presentation**

 OCS use will be summarised only for the subjects enrolled into study 201312 from previous OCS reduction study MEA115575. This analysis will present the median OCS Dose (mg/day) during the current and preceding study periods (from studies MEA115575 and MEA115661) to assess if the reduction in OCS use has been maintained.

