- e) Their optimized dose at randomization in MEA115575 was ≥ 10 mg of prednisone
- f) ≥ 1 or more hospitalization for asthma exacerbation in the 12 months prior to screening for MEA115575

Those subjects that do **not** meet the definition of potentially life threatening asthma must be assessed as having serious debilitating asthma.

Subjects enrolled in MEA115588 or MEA115575 must meet the following criteria:

At randomisation of MEA115588 or MEA115575 must have:

- g) A % predicted FEV1 of $\leq 50\%$ and either
- h) ACQ5 score of ≥ 3 or
- i) SGRQ score of ≥ 60

7. **Clinical Benefit:** Subjects must have experienced documented clinical benefit to enroll. Subjects must meet the following criteria demonstrating clinical benefit:

Subjects enrolled in MEA115588 who received mepolizumab must meet all of the following criteria:

- a) Subject must have had a reduction in their exacerbation frequency by $\geq 50\%$ during MEA115588. The baseline for comparison is the total number of exacerbations reported in the 12 months prior to screening for MEA115588.
- b) The investigator confirms that the subject demonstrated improvement during MEA115588.

Subjects enrolled in MEA115588 who received placebo must meet all of the following criteria:

- c) Subject must have had a reduction in their exacerbation frequency by $\geq 50\%$ during the first 8 months of MEA115661. The baseline for comparison is the total number of exacerbations reported in the 12 months prior to screening for MEA115588.
- d) The investigator confirms that the subject demonstrated improvement during MEA115661

Subjects enrolled in MEA115575 who received mepolizumab must meet all of the following criteria:

- e) Subject must have reduced their oral corticosteroid dose by $\geq 50\%$ during MEA115575. The baseline for comparison is the subject's optimized OCS dose at randomization in MEA115575
- f) The investigator confirms that the subject demonstrated improvement during MEA115575.

Subjects enrolled in MEA115575 who received placebo must meet all of the following criteria:

- g) Subject must have reduced their oral corticosteroid dose at randomization by $\geq 50\%$ in the first 6 months of MEA115661. The baseline for comparison is the subject's optimized OCS dose at randomization in MEA115575.
- h) The investigator confirms that the subject demonstrated improvement during MEA115661.

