### 11.10.8. Efficacy Tables

Efficac	Efficacy: Tables						
No.	Population	IDSL / Example Shell	Title	Programming Notes	Deliverable [Priority]		
Exacer	bations						
3.1	AT	SHELL	Overview of All Exacerbations	See Efficacy Table 2.61 (200862 'final' reporting effort)	SAC		
3.2	AT	SHELL	Summary of Frequency of All Exacerbations	See Efficacy Table 2.62 (200862 'final' reporting effort)	SAC		
3.3	AT	SHELL	Annualised Rate of Exacerbations	See Efficacy Table 2.64 (200862 'final' reporting effort)	SAC		
3.4	AT	SHELL	Overview of Exacerbation Rate by Treatment Allocated Within MEA115588 and Study Period (MEA115588, MEA115661 and 201312 combined)	See Efficacy Table 6.15 (MEA115661 'final' reporting effort)	SAC		
3.5	AT	SHELL	Analysis of Time to First Exacerbation	See Efficacy Table 2.68 (200862 'final' reporting effort)	SAC		
3.6	AT	SHELL	Summary of Frequency of Exacerbations Requiring Hospitalisation or Emergency Department visits	See Efficacy Table 2.62 (200862 'final' reporting effort)	SAC		
3.7	AT	SHELL	Annualised Rate of Exacerbations Requiring Hospitalisation or Emergency Department visits	See Efficacy Table 2.64 (200862 'final' reporting effort)	SAC		
3.8	AT	SHELL	Summary of Frequency of Exacerbations Requiring Hospitalisation	See Efficacy Table 2.62 (200862 'final' reporting effort)	SAC		
3.9	AT	SHELL	Annualised Rate of Exacerbations Requiring Hospitalisation	See Efficacy Table 2.64 (200862 'final' reporting effort)	SAC		
Asthma	a Control Quest	tionnaire (ACQ-5)					
3.10	AT	SHELL	Summary of Asthma Control Questionnaire (ACQ-5) Score	See Efficacy Table 2.34 (200862 'final' reporting effort)	SAC		

201312

Efficacy: Tables								
No.	Population	IDSL / Example Shell	Title	Programming Notes	Deliverable [Priority]			
Pre – B	ronchodilator I	EV1						
3.11	AT	SHELL	Summary of Clinic Pre-Bronchodilator FEV1 (mL)	See Efficacy Table 2.27 (200862 'final' reporting effort)	SAC			
Oral Co	Oral Corticosteroid Use							
3.12	AT	SHELL	Summary of OCS Dose (mg/day) During Each Reporting Period by Treatment Allocated Within MEA115575 and Study Period (MEA115588, MEA115661 and 201312 combined)	See Efficacy Table 6.16 (MEA115661 'final' reporting effort)	SAC			

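### Maintenance of the steroid reduction is to be judged by a group median OCS dose, with no per-subject measure stated, and the Table 3.12 title lists MEA115588 where the SAP text says MEA115575

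*SAP*

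**What the plan says.** SAP 8.2.1 lists oral corticosteroid dose among the secondary efficacy variables. Sections 8.2.2 and 8.2.5.1 limit the summary to one subset: "OCS use will be summarised only for the subjects enrolled into study 201312 from previous OCS reduction study MEA115575". The measure is then named: "This analysis will present the median OCS Dose (mg/day) during the current and preceding study periods", drawing on MEA115575 and MEA115661 as the preceding studies. The stated purpose is "to assess if the reduction in OCS use has been maintained".

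The protocol defines the OCS benefit per subject (4.2, criterion 7). For former mepolizumab subjects from MEA115575, item 7e reads "Subject must have reduced their oral corticosteroid dose by" at least 50% during that study. For former placebo subjects, item 7g places the same 50% reduction in the first 6 months of MEA115661. The reference dose is the same in both: "The baseline for comparison is the subject's optimized OCS dose at randomization in MEA115575". Criterion 8 also admits subjects who do not meet criterion 7.

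The output is Table 3.12 (SAP 11.10.8). Its title reports OCS dose for each reporting period "by Treatment Allocated Within MEA115575 and Study Period (MEA115588, MEA115661 and 201312 combined".

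**The concern.** The question in the SAP is about keeping a reduction, and the protocol defines that reduction one subject at a time. A group median of absolute dose does not show how many subjects kept theirs. It does not respond to increases among subjects already above it, and it stays at 0 mg while more than half take none. The study has one arm and no hypotheses (protocol 8.1), so this descriptive table is the planned evidence on the question. A stable median could be reported as a maintained reduction although a sizeable minority had lost it.

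The make-up of the group also changes. SAP 11.6.1 expects no completers, with all subjects eventually withdrawing, so the median in later reporting periods can shift because of who is left. Percent change from each subject's own fixed reference dose keeps the comparison paired.

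The title of Table 3.12 is a smaller matter. Programmed literally, it would call for a period from a study these subjects did not come from and leave out the one that holds their reference dose.

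**Working it through.** The plan states no figure for this endpoint, so there is none to reproduce. The documents give neither the size of the MEA115575 subset nor any dose distribution. All doses below are assumptions for illustration.

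**1. Worst-case bound (no dose assumption).** With n subjects, ceil(n/2) - 1 of them can rise to any dose without moving the sample median, provided they are already above it or tied with it.

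| n | ceil(n/2) - 1 | share |
|---|---|---|
| 25 | 12 | 48.0% |
| 50 | 24 | 48.0% |
| 100 | 49 | 49.0% |
| 375 (approximate whole study, protocol 4.1) | 187 | 49.9% |

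**2. What the bound looks like.** Let 100 subjects go from 10 to 5 mg/day and let 49 return to 10 mg/day.
- Median: 5 before, 5 after. With 50 returning it becomes (5 + 10)/2 = 7.5.
- Mean: 5.00 before; (51 × 5 + 49 × 10)/100 = 7.45 after.
- Share still at least 50% below the reference dose: 100% before, 51% after.

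Ties at zero act in the same way. If all 100 are at 0 mg and 49 return to 10 mg, the median stays 0 and the mean becomes 4.9.

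**3. A mixed-dose case.** Let the reference dose be 12.5 mg for all 100 subjects, with 40, 20, 20 and 20 of them now at 0, 2.5, 5 and 6.25 mg. All have at least a 50% reduction. If the 40 above the median return to 12.5 mg, the median stays 2.5 and the share keeping the reduction falls from 100% to 60%. The mean rises from 2.75 to 5.50.

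**4. When relapse is unrelated to dose.** In the mixed-dose case the median stays 2.5 only if at least 51 subjects remain at or below 2.5 mg, so at most 9 of those 60 may relapse. With 20 of 100 relapsing at random, the hypergeometric probability of 9 or fewer among the 60 is 0.10. With 30 relapsing it is below 0.001.

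A simulation with more varied doses agrees (n = 100, 400 replicates, full doses 5 to 30 mg, reductions 50 to 100%). Average medians in mg/day were:

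| Random relapse | No subject at 0 mg | About 40% at 0 mg |
|---|---|---|
| 20% | 3.75 to 4.89 | 1.67 to 2.93 |
| 40% | 3.77 to 6.71 | 1.70 to 5.20 |

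The median is therefore blind mainly when relapse is concentrated at or above it, or when many doses are tied.

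**5. Table 3.12 title against the text.** SAP 8.2.2 and 8.2.5.1 name MEA115575 and MEA115661 as the preceding studies. The title splits treatment by MEA115575 allocation, which agrees, but its study-period list begins with MEA115588, which does not. Table 3.4 is titled "Overview of Exacerbation Rate by Treatment Allocated Within MEA115588 and Study Period (MEA115588, MEA115661 and 201312 combined"). That list is right there, because Table 3.4 concerns MEA115588 entrants. The list in 3.12 looks carried over from it.

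**The case against.** The strongest reply is that the median may not stand alone. SAP 8.2.5 says that secondary endpoints are summarised with descriptive statistics unless otherwise specified. Table 3.12 is laid out by reporting period and follows an existing MEA115661 table, and the shells are available only on request. Means or quartiles of dose may well appear. In step 2 the mean moves from 5.00 to 7.45 and the upper quartile from 5 to 10, so a careful reader would see that something had changed. This stands, and it rules out saying that the median will be the only statistic shown. But no summary of the dose distribution counts the subjects who kept their own reduction.

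A reader might infer that the plan will probably hide relapse in nearly half the subjects. The documents do not support that. The near-50% figure is a limit needing a particular pattern of relapse, and step 4 shows that random relapse of 20% or more usually moves the median.

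A reader might also take MEA115575 to be where every subject achieved the reduction. Item 7g places it in MEA115661 for former placebo subjects. MEA115575 supplies the reference dose for all, so the title still needs correcting.

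Third, a plain count of subjects at least 50% below the reference would misclassify some. Criterion 8 entrants may never have had the reduction, and others may have lost it before 201312 began. This is a fair limit on any retention measure, and the denominator must deal with it.

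Finally, OCS dose is not among the protocol's endpoints; the SAP adds it as a descriptive summary. The title slip is close to clerical, since the text is right in both places. Both facts limit the weight of the point.

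**Conclusion.** The point holds as a mismatch between question and measure. The SAP asks whether a reduction was maintained and names a group median by study period, while criterion 7 defines the reduction within each subject. No per-subject measure or criterion for maintenance is stated.

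The possible size is bounded at ceil(n/2) - 1 subjects returning to full dose with the median unchanged, or 48% to 49.9% for the values of n tabulated. The bound needs no assumption about dose, only that those who relapse sit at or above the median or are tied with it. It is not a forecast. The 51% and 60% retention figures rest on invented doses and on everyone having the reduction at the start.

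The title of Table 3.12 conflicts with the SAP text in its study-period list only; its treatment-allocation part is right. No primary analysis or hypothesis test is affected. This is an inexpensive improvement to a secondary descriptive output and should be made.

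**What to change.** In SAP 8.2.2, 8.2.5.1 and Table 3.12, keep the median and add, by reporting period:
- the per-subject percent change from the optimized OCS dose at randomization in MEA115575;
- n (%) with exact 95% confidence interval still at least 50% below that dose. The denominator is MEA115575 entrants who had that reduction at entry to 201312 and still have on-treatment data in the period, and it should be shown in the table.

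Report criterion 8 entrants and others without the reduction at entry separately, so that they are not counted as losses during 201312.

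In the Table 3.12 title, change the study-period list from MEA115588 to MEA115575, giving MEA115575, MEA115661 and 201312.

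No new data are needed. Corticosteroid doses and dose changes are already recorded (protocol 5.7.1), and the optimized dose was already required for eligibility. The real cost is programming. SAP 11.5.2 derives only a baseline OCS daily dose, so a rule is needed for the on-treatment maintenance daily dose in each period, one that excludes steroid bursts given for exacerbations.

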### 9. PHARMACODYNAMIC ANALYSIS

### 9.1. Pharmacodynamic Analyses

### 9.1.1. Endpoint / Variables

The pharmacodynamic variable considered is blood eosinophils.

#### 9.1.2. Summary Measure

Blood eosinophil count and ratio to baseline will be summarised by visit.

### 9.1.3. Population of Interest

The pharmacodynamic analyses will be based on the AT population, unless otherwise specified.

### 9.1.4. Strategy for Intercurrent (Post-Randomization) Events

Only on-treatment blood eosinophils will be analysed (See Section 11.3.1).

### 9.1.5. Statistical Analyses / Methods

Details of the planned displays are provided in Appendix 10: List of Data Displays and will be based on GSK Data Standards and statistical principles.

Unless otherwise specified, endpoints / variables defined in Section 9.1.1 will be summarised using descriptive statistics.

#### 9.1.5.1. Statistical Methodology Specification

End	point / Variables
•	Ratio to baseline in blood eosinophil count
Data	a Specification
•	A log-transformation will be applied to blood eosinophil count data prior to summarising the data.
•	If a blood eosinophil count of zero is reported, it will be imputed with half of the lowest possible blood eosinophil count, where applicable, prior to log transforming the data (Note: this imputation has typically been 0.5 * 0.01 GI/L = 0.005 GI/L for previous mepolizumab studies).
Res	ults Presentation

- Blood eosinophil count and ratio to baseline will be summarised by visit.
- Geometric mean and standard deviation (on natural log scale) will be summarised.

### 11. **APPENDICES**

### **11.1.** Appendix 1: Schedule of Activities

#### Table 1Time and Events Table

Procedures	Week 52 of MEA115661 						Treatme	e nt Perio	d (Visit V	/indow is	s ± 1 wee	k)				
Visit	1	2	3	4	5	6	7	8	9	10	11	12	13	14	15	16
Week of study	0	4	8	12	16	20	24	28	32	36	40	44	48	52	56	60
Written Informed Consent	X															
Medical History Changes	X	i i				1						j.		i i		
Smoking Status	X					l. J							2 2			-
Inclusion/Exclusion	X															
Criteria																
Safety Assessments	A2 22					•					л. К					
Concomitant Medication	X	X	Х	Х	X	X	X	X	X	X	X	X	Х	Х	X	X
Physical Examination	X															
Vital Signs	X	Х	Х	Х	Х	X	X	Х	Х	X	X	Х	Х	Х	X	Х
12-lead ECG	X		о 2		20 20		Х						X			
Adverse Events	X	X	X	Х	X	X	Х	Х	Х	X	Х	Х	X	Х	X	X
Serious Adverse Events	X	X	X	X	Х	X	Х	X	X	X	X	X	X	X	X	X
Laboratory Assessments	2			.	97) -	о. — ;;		· · · · · ·			2		12. 			
Immunogenicity	X		19 1		29 	en e		ni e		10 S	2		X	12 12		2
Hematology	X		93 17				X						X			
Chemistry	X		14				X					x	X	.x x		
Liver Analytes	X						Х						Х			
Pregnancy Test 	U	U	U	U	U	U	U	U	U	U	U	U	U	U	U	U
Efficacy Assessments																
Exacerbation review	X	Х	Х	Х	Х	X	Х	X	X	X	X	X	Х	Х	X	Х
Asthma Control	X			Х			X			X		5 m	Х			X
Questionnaire-5			1.		12					1			0.000			
Spirometry	X						X						Х			

1. Before entry in to study 201312, determine which scenario the subject is best classified as and perform the relevant procedures as defined in Section 11.5.1 of the Protocol and the SPM.

2. All laboratory assessments to be completed prior to dosing

3. Pregnancy test (all females of childbearing potential) U = Urine

Procedures	Week 52 of MEA115661 						Treatme	ent Perio	d (Visit W	/indow is	s ± 1 wee	k)				
Visit	1	2	3	4	5	6	7	8	9	10	11	12	13	14	15	16
Week of study	0	4	8	12	16	20	24	28	32	36	40	44	48	52	56	60
Worksheets/IP/eCRF	90 - S								1	30 S	a 83		6			
Administer Mepolizumab 100mg SC	X	Х	Х	X	X	X	X	X	х	Х	X	Х	X	X	X	Х
Dispense paper worksheet	X	X	Х	X	Х	X	X	X	X	Х	X	X	X	X	X	X
Collect paper worksheet		X	X	Х	X	X	X	X	X	X	X	X	X	X	Х	X
Register IVRS/IWRS	X	X	X	X	X	X	X	X	X	X	X	X	X	X	X	X
Complete eCRF	X	Х	Х	X	X	X	X	Х	Х	X	X	X	Х	Х	X	Х

1. Before entry in to study 201312, determine which scenario the subject is best classified as and perform the relevant procedures as defined in Section 11.5.1 of the Protocol and the SPM.

2. All laboratory assessments to be completed prior to dosing

3. Pregnancy test (all females of childbearing potential) U = Urine

#### 201312

Procedures						Treatme	ent Perio	d (Visit W	indow is	±1 wee	k)				_
Visit	17	18	19	20	21	22	23	24	25	26	27	28	29	30	31
Week of study	64	68	72	76	80	84	88	92	96	100	104	108	112	116	120
Safety Assessments						10									
Concomitant Medication	Х	Х	Х	Х	X	X	Х	Х	X	Х	Х	X	Х	X	X
Physical Examination			20.00		10000		-							10010	
Vital Signs	X	Х	Х	X	X	X	X	Х	X	Х	X	X	X	X	X
12-lead ECG	-		Х					_	X						
Adverse Events	X	X	Х	X	X	Х	Х	Х	X	Х	Х	X	Х	Х	X
Serious Adverse Events	X	Х	X	X	X	Х	X	Х	X	Х	X	X	X	X	X
Laboratory Assessments	2			•		•									
Immunogenicity				1					X				1		
Hematology	Ĵ.		X						X						X
Chemistry			Х						X						X
Liver Analytes	32 		X						X						X
Pregnancy Test 	U	U	U	U	U	U	U	U	U	U	U	U	U	U	U
Efficacy Assessments							!		•				•	'	
Exacerbation review	X	Х	X	X	X	X	X	Х	X	Х	X	X	X	X	X
Asthma Control Questionnaire-5			X			X			X		-	X			X
Spirometry	1		X			1			X						X
Worksheets/IP/eCRF				1); 		10		4.0 ())							
Administer Mepolizumab 100mg SC	Х	Х	Х	X	X	X	Х	Х	X	X	X	X	X	X	X
Dispense paper worksheet	X	Х	Х	X	X	X	х	X	X	X	Х	X	X	X	X
Collect paper worksheet	X	Х	Х	X	X	X	Х	X	X	Х	X	X	X	X	X
Register IVRS/IWRS	X	X	X	X	X	X	X	X	X	X	X	X	X	X	X
Complete eCRF	X	Х	Х	X	X	X	X	Х	X	Х	X	X	X	X	X

All laboratory assessments to be completed prior to dosing
 Pregnancy test (all females of childbearing potential) U = Urine

#### 2017N348509 00

